#### Randomized, Double-Blind, Placebo-Controlled Part:

A total of 2000 subjects will be randomized to receive Aramchol or matching placebo employing a 2:1 randomization scheme, respectively.

The Randomized, Double-Blind, Placebo-Controlled Part consists of 2 phases; an initial phase with a Histology-Based endpoint, and a subsequent phase with a Clinically-Based endpoint. Throughout the duration of both study phases, subjects will be treated with either Aramchol or matching placebo according to randomization scheme generated prior to study initiation. The study phases are:

#### Histology-Based phase:

The statistical analysis of the Histology-Based primary endpoint will be conducted when the initially randomized 1000 subjects have completed the week 72 visit or terminated early. This analysis will serve as the basis for submission of a marketing authorization application under regulatory provisions of accelerated/conditional approval.

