- The 3rd data assessment will occur at a time when approximately twothirds of the study population have undergone the post-baseline liver biopsy. Assessments will include analysis of histological endpoints and NITs.
- The 4th data assessment for assessing the kinetics of the histological outcome measures and NITs for the duration of 24, 48 and 72 weeks will be conducted at the time when all randomized subjects have undergone the post-baseline liver biopsy.
- A potentially 5th data assessment for further assessing the kinetics of the histological outcome measures and NITs for treatment duration of 24, 48 and 72 weeks and potentially following a 2nd post-baseline biopsy at weeks 72 or 96 or 120, respectively, will be conducted at the time when the last randomized subjects have underwent the last post-baseline liver biopsy.

The planned sample size of a total of 150 subjects is considered appropriate for assessing the kinetics of histological outcome measures and NITs associated with NASH and fibrosis for the treatment duration of 24, 48 and 72 weeks.

The overall alpha level for the Open-Label Part is 0.05 using 2-tailed tests. No multiplicity adjustment is planned as this study part is exploratory in nature.

•

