#### **Schedule of Statistical Analyses:**

Statistical analyses of efficacy endpoints are planned to be performed at two study milestones:

- The Histology-Based primary endpoint will be analyzed at the time when the initially randomized 1000 subjects have performed the week 72 visit or terminated early.
- The Clinically-Based primary endpoint will be analyzed at EoS, when all 2000 subjects planned to be randomized into this study will receive Aramchol or matching placebo until EoS which will occur at the time when a total of 380 subjects will experience at least 1 pre-specified clinical event or at 5 years from last subject randomization, whichever comes first.

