# 3.4 Rationale for Study Design, Dose and Population

#### 3.4.1 Study Rationale

The current study is composed of two parts:

An Open-Label Part to evaluate the safety and PK of Aramchol 300 mg BID in subjects with NASH and liver fibrosis and to explore the kinetics of histological outcomes and NITs associated with NASH and liver fibrosis for the treatment duration of 24, 48 and 72 weeks. The study population includes subjects with NASH and liver fibrosis stage 1-3, subjects with NASH who may or may not be overweight and subjects with NASH who may or may not have T2DM or be pre-diabetic. PK and safety data and information on the kinetics of histological outcomes and NITs from this Open-label Part will be summarized in support of regulatory submissions. However, histological outcomes and clinical events from the Open-Label Part will not be considered for the Histology-Based primary endpoint and the Clinically-Based primary

endpoint of the Randomized, Double-Blind, Placebo-controlled part of the study. Clinical events will instead be reported as safety data.

A Randomized, Double-Blind, Placebo-Controlled Part to evaluate the safety and efficacy of Aramchol 300 mg BID to support regulatory approval. The study population for this part includes subjects with NASH and liver fibrosis stage 2 and 3 who are overweight and are either pre-diabetic or have T2DM. The Randomized, Double-blind, Placebo-Controlled Part of the study is generally consistent with FDA Guidance for Industry – Noncirrhotic Nonalcoholic Steatohepatitis with Liver Fibrosis: Developing Drugs for Treatment (December 2018) 13 and EMA Reflection paper on regulatory requirements for the development of medicinal products for chronic noninfectious liver diseases (PBC, PSC, NASH) (November 2018)14, and is intended to demonstrate the effectiveness and safety of Aramchol to support regulatory approval. Consistent with regulatory guidance there are two primary endpoints for this part of the study:

- ✓ A Histology-Based primary endpoint that will be analyzed after 1000 subjects have completed 72 weeks. The Histology-Based endpoint data will serve as the basis for the submission of a marketing authorization application under regulatory provisions of accelerated/conditional approval based on a surrogate endpoint.
- ✓ The Clinically-Based primary endpoint that will be analyzed at EoS and will provide confirmation of clinical benefit based on a clinical outcomes endpoint.

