# Randomized, Double-Blind, Placebo-Controlled Part:

[figure not shown]
- Week 72 biopsy: may be performed from 2 weeks prior to week 72 visit and up to 6 weeks after week 72
- 5-year biopsy: may be performed at the 5-year visit± 8 weeks

[figure not shown]

[figure not shown]

[figure not shown]

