### Liver biopsy:

- 72-week liver biopsy may be performed from 2 weeks prior to the week 72 visit and up to 6 weeks after week 72.
- 5-year liver biopsy should occur within 8 weeks (prior to or after) of the 5-year visit, unless there is an available biopsy within the past year.

Coagulation results should be within normal ranges before the biopsy is performed. If the study subject is taking any anticoagulant it should be discontinued a sufficient amount of time before the biopsy to avoid any undue bleeding. NSAIDs are prohibited 48 hours prior to the biopsy.

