### **ARMOR Study**

All liver biopsies will be centrally evaluated while the assessor is blinded to treatment assignment as well as to other parameters including site and sequence or indication (screening biopsy or week 72 biopsy or biopsy due to suspicion to progression to cirrhosis).

Adjudication committee members will be blinded to treatment assignment.

The DMC will consist of independent physicians with expertise in liver disease and internal medicine and an independent biostatistician, all with prior experience and expertise in clinical trials. An Independent Unblinded Statistician will prepare the reports for review by the DMC.

Unblinded safety reports if required for regulatory submissions as well as reporting of Suspected Unexpected Serious Adverse Reactions (SUSARs) will be handled by dedicated personnel. For these purposes, unblinding will be performed on an individual subject's basis. The Sponsor will remain blinded to that individual subject's treatment assignment.

In case of emergency code breaking, when the study drug assignment is needed to make treatment decisions for the subject, the Investigator may unblind the subject's drug assignment. The unblinded subject will be withdrawn from the study. In such cases of emergency unblinding, subject's treatment assignment will not be revealed to the Sponsor.

Analysis of the Histology-Based primary endpoint will be conducted when 1000 subjects complete their initial treatment period of 72 weeks (or terminated earlier). For the purpose of the conduct of these analyses which may be followed by a marketing authorization application, the Sponsor will establish a special taskforce firewalled from the study team. The taskforce will be led by a Sponsor management team member not directly involved in the ongoing management of the study. To maintain the integrity of the final post-Week 72 analyses, only a minimal number of personnel belonging to this taskforce will be exposed to the subject -level data, primarily to facilitate regulatory filings and required public disclosures.

Furthermore, study subjects, Investigators, and the Sponsor personnel involved in the ongoing study management and any personnel involved in subjects' assessments, monitoring, and Data Management will remain blinded to treatment assignment.

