## 11.2.2 Study Primary Endpoints

The primary efficacy endpoints for this study are:

- Histology-Based: The Histology-Based primary endpoint will be derived from the week-72 biopsy of the initial 1000 subjects as compared to baseline biopsy and will use:
  - ✓ Resolution of NASH defined as the Proportion (%) of subjects with resolution of NASH (defined by Ballooning of 0 and inflammation 0-1) and no worsening of liver fibrosis on NASH CRN fibrosis score (≥ 1 stage increase).

OR

[figure not shown]
✓ Improvement in Fibrosis defined as the Proportion (%) of subjects with improvement in liver fibrosis greater than or equal to one stage (NASH CRN fibrosis score) and no worsening of steatohepatitis (defined as no increase in NAS for ballooning, inflammation or steatosis)

[figure not shown]
- Clinically-Based: The Clinically-Based primary endpoint is the time to first occurrence of any of the following adjudicated events:
  - ✓ All-cause mortality
  - ✓ Liver transplant
  - ✓ Histological progression to cirrhosis
  - ✓ MELD score >15 if baseline MELD score was <12
    

  - ✓ Hospitalization due to hepatic decompensation event(s) including:
    - Hepatic encephalopathy grade ≥2 (as assessed by West Haven scale)
    - Variceal bleeding
    - New onset ascites requiring treatment
    - Spontaneous bacterial peritonitis as assessed by either positive cell culture or cell count

Events will be adjudicated by an independent adjudication committee.

[figure not shown]

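### The week-72 histology analysis is timed on the visit, 72 weeks or early termination, not on the biopsy, so in-window biopsies could still be pending when it is due

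*Combined protocol and SAP*

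**What the plan says.** **The milestone** appears in four visible places:

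- Synopsis, Schedule of Statistical Analyses: "at the time when the initially randomized 1000 subjects have performed the week 72 visit or terminated early".
- Section 3.4.1: "A Histology-Based primary endpoint that will be analyzed after 1000 subjects have completed 72 weeks".
- Section 5.1, Histology-Based phase: "will be conducted when the initially randomized 1000 subjects have completed the week 72 visit or terminated early".
- Section 8.4.3: the analysis "will be conducted when 1000 subjects complete their initial treatment period of 72 weeks (or terminated earlier").

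**The outcome.** Section 11.2.2 says that the endpoint "will be derived from the week-72 biopsy of the initial 1000 subjects as compared to baseline biopsy". Section 8.2.5 sets the window: "72-week liver biopsy may be performed from 2 weeks prior to the week 72 visit and up to 6 weeks after week 72". The biopsy-timing note that follows the early-discontinuation text of section 8.1, and section 9.1.2, give the same limits. The estimand in section 11.2.8.1 accepts the same range, so a biopsy at week 78 is a valid primary observation.

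**Missing biopsies.** Section 11.2.9.2 handles missing week-72 values by deterministic rules together with multiple imputation. No visible text separates a biopsy that is not yet due from one that is missing.

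**Early discontinuation.** Section 8.1 distinguishes stopping treatment while still attending visits (ETD) from leaving the study (ESD). Section 10.1.2 equates early termination with ESD.

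**The concern.** The clock for the analysis and the clock for the outcome differ. A subject can meet any of the four statements with a protocol-compliant biopsy still booked. If the analysis is run when the milestone is met, an outcome that could have been observed is imputed instead.

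The analysis is meant to support an application for accelerated or conditional approval. Once it is done, a firewalled taskforce holds subject-level data and group results may be made public (section 8.4.3). A biopsy that arrives afterwards could be added only by people who already know the result.

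The four statements also disagree with each other. The synopsis and section 5.1 name the first 1000 randomised; sections 3.4.1 and 8.4.3 refer only to 1000 subjects. Section 3.4.1 has no clause for early termination. Section 8.4.3 links termination to the treatment period, which leaves open whether a subject who is off drug but still followed is regarded as finished.

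**Working it through.** The visible text gives no figure to reproduce: sections 11.2.3 to 11.2.6 are not shown, and the accrual rate is not stated. The size of the gap therefore rests on assumptions.

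**Lag.** Latest valid biopsy minus milestone = week 78 - week 72 = 6 weeks.

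**Assumptions.** Uniform accrual of the first 1000 subjects, no dropout, visits exactly at week 72, and a month of 52/12 weeks.

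**Ceiling.** This is everyone who passed week 72 within the 6 weeks before the last of the 1000 does so, i.e. accrual per week x 6:

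| Accrual of first 1000 | Weeks | Per week | x 6 weeks |
|---|---|---|---|
| 18 months | 78 | 12.8 | 77 |
| 24 months | 104 | 9.6 | 58 |
| 36 months | 156 | 6.4 | 38 |

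This is reached only if every one of these subjects has the biopsy on the last permitted day.

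**Even spread over the window.** If biopsies fall evenly over the 8 weeks from -2 to +6, a subject who is t weeks past week 72 is still pending with probability (6 - t)/8. Summed over t from 0 to 6, this is 6²/(2 x 8) = 2.25 weeks of accrual:

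- 18 months: 12.8 x 2.25 = 29 (2.9% of 1000)
- 24 months: 9.6 x 2.25 = 22 (2.2%)
- 36 months: 6.4 x 2.25 = 14 (1.4%)

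**Precision.** If the pending subjects contributed nothing at all, the standard error would grow by a factor √(1000/(1000 - k)): √(1000/971) = 1.015 for k = 29 and √(1000/923) = 1.041 for k = 77.

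**Power, as an illustration only.** Take the Phase 2b fibrosis rates in section 3.2 (29.5% on 600 mg, 17.5% on placebo), 2:1 allocation, and two-sided alpha 0.01 (half of the 0.02 assigned to this endpoint). Use the normal approximation Φ[(d - z·s₀)/s₁], with s₀ the pooled and s₁ the unpooled standard error, d = 0.12 and z = 2.576.

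- 1000 biopsies: s₀ = 0.0292, s₁ = 0.0273, power 94.9%.
- 885 biopsies: s₀ = 0.0311, s₁ = 0.0290, power 91.6%.

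The second line removes 115 subjects, the ceiling under a faster 12-month accrual (1000/52 = 19.2 per week; x 6 = 115). Even that extreme costs about 3 points.

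**The case against.** **The visit may include the biopsy.** Section 8.2.5 lists what is done at scheduled visits, and the week-72 biopsy stands in that section, so a visit with its biopsy outstanding might not count as completed. This reading is possible but not secure. The same section dates the biopsy relative to the visit, which makes them two events, and section 8.2.8 keeps a subject who refuses a biopsy in the study. The synopsis asks only that the visit has been performed.

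**A milestone is not a data cut.** No text says that data are frozen on the day of the last visit, and omitting in-window biopsies would contradict the estimand. Sections 11.2.3 to 11.2.6 and the separate detailed SAP are not visible, and a cut-off rule may be there. This stands: the documents do not show that the analysis *would* run without these biopsies, only that the visible wording allows it.

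**Subjects off treatment.** A reader might infer from section 8.4.3 that someone who stopped drug at week 60 is already closed, 10 to 18 weeks before the biopsy is due at weeks 70 to 78. The documents do not support this as the plan's rule. Section 10.1.2 equates early termination with ESD, and section 8.1 keeps ETD subjects on scheduled visits. Section 8.2.8 also provides for a biopsy at the treatment discontinuation visit or a later scheduled visit. What remains is an ambiguity in section 8.4.3.

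**The Open-Label comparison.** That part ties its fourth assessment to the biopsy: it "will be conducted at the time when all randomized subjects have undergone the post-baseline liver biopsy". This shows that the sponsor can write a biopsy-based trigger. It is not a model to copy, because it has no clause for refusal or dropout and might never be met literally.

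**Conclusion.** The mismatch is real on the visible text. All four statements of the milestone rest on the week-72 visit, 72 weeks or early termination, while the primary outcome may validly arrive up to 6 weeks later.

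The effect is small. Under the accrual assumptions above, about 14 to 29 biopsies (1.4-2.9% of the primary set) would be pending if timing is even over the window, and 38 to 77 at the very most. A reader might take the latter as a loss of 4-8% of the outcomes; they are ceilings, not expectations. Nor do the documents support a claim of serious bias or an underpowered trial. Biopsies pending because of late enrolment are missing for a calendar reason, so the main costs are precision and imputation that waiting would have avoided.

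The conclusion depends on no cut-off rule being present in the sections and SAP that cannot be seen. If one is there, the four statements still need to be aligned with it.

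**What to change.** Use one milestone in the synopsis (Schedule of Statistical Analyses) and in sections 3.4.1, 5.1 and 8.4.3, and in section 11.2.3 and the SAP if they repeat it. The data cut is made when each of the first 1000 randomised subjects

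- has had the week-72 biopsy, or
- has passed week 78 without one, or
- has left the study (ESD).

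State that early termination in this rule means ESD, and that stopping treatment alone (ETD) does not close a subject.

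The cost is a wording change and a delay of at most about 6 weeks. Sample size, alpha and endpoint definition are unchanged. Section 8.4.3 already plans a SAP amendment before the blind is lifted for the histology data, which is a natural place for the SAP text.

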#### Clinically-Based phase:

All 2000 subjects planned to be randomized into this study will receive Aramchol or matching placebo until End-of-Study (EoS) which will occur at the time when a total of 380 subjects will experience at least 1 pre-specified clinical event or at 5 years from last subject's randomization, whichever comes first.

Extension study: Subjects that complete 7 years in the study or that are ongoing at EoS will be provided the option to receive Aramchol treatment in an open-label extension. The extension study will be detailed under a separate protocol

#### 6 STUDY POPULATION

The Randomized, Double-Blind, Placebo-Controlled Part will enroll adult subjects, 18–75 years old, with NASH and fibrosis (F2-F3) confirmed by liver histology who are overweight or obese and have prediabetes or type 2 diabetes.

The Open-Label Part intends to assess the safety, PK and treatment response kinetics of Aramchol 300mg BID in a broader population, including subjects with fibrosis stage 1, subjects who are not overweight, and subjects who do not have T2DM.

In both study parts, patients with cirrhosis, abnormal synthetic liver function and history or presence of decompensated liver disease will not be enrolled to the study.

#### 6.1 Inclusion Criteria

The inclusion criteria for the Open-Label Part are the same as those of the Randomized, Double-Blind, Placebo-Controlled Part with the exception of fibrosis stage (the Open-Label Part allows enrollment of subjects with fibrosis stage 1), weight (the Open-Label Part allows enrollment of subjects who are not overweight) and Type-2 diabetes mellitus (the Open-Label Part allows enrollment of subjects who are not prediabetic or subjects who do not have Type-2 diabetes mellitus

In order to be eligible to the study, subjects must meet all the following criteria:

- 1. Male or female age 18 to 75 years (inclusive at first Screening visit)
- Histological confirmation of NASH on a diagnostic liver biopsy by central reading of the slides

- 3. Total NAS Score 4 or more with at least 1 in each component of the NAS Score (steatosis ≥1 AND inflammation ≥1 AND ballooning ≥1)
- 4. Fibrosis Stage must be 2 or 3
  - Open-Label Part only: 30 subjects with fibrosis stage 1 may be included
- 5.
- 6. Body mass index (BMI)
  - Open-Label Part: ≤ 40 kg/m²
  - Randomized, Double-Blind, Placebo-Controlled Part: between 25kg/m^2 and 40 kg/m^2

informed consent.

7.

8.	Randomized, Double-Blind, Placebo-Controlled Part only: Type 2 diabetes mellitus or prediabetes: Type 2 diabetes diagnosis must be established and documented prior to screening. For prediabetes, unless pharmacologically treated, the diagnosis should be verified by screening results (by central lab) according to the American Diabetes Association criteria, which requires at least one of the following 3 criteria:
9. 10.	For subjects with type 2 diabetes, glycemia must be controlled  Negative blood pregnancy test at study entry for females of childbearing potential
11.	confirmed by central laboratory
12.	Able to understand the nature of the study and to provide signature of the written

#### 7 CONCOMITANT MEDICATIONS AND SPECIAL WARNINGS

## 7.1 Allowed Concomitant Medications During the Study

Any medications, excluding those mentioned in Section 7.2 may be given concomitantly as needed for the subject's welfare. Administration of all medications, including indication, dose, start and end date including dose modification, frequency, and route of administration will be recorded in the source documentation file and in the electronic Case Report Form (eCRF). Concomitant medications will be discussed and documented at each visit.

Local (including injection, topical and inhaled) steroids are allowed

# 7.2 Disallowed Concomitant Medications During the Study

Investigational products are disallowed during the study.

Alternative treatments should not be initiated during study.

Drugs that are approved for the treatment of NASH (in the event that drugs are approved during the course of the study) are disallowed during the study. Therefore, subjects initiating such drugs should be discontinued from the study. A liver biopsy is recommended at end of study unless there is an available biopsy within the past 6 months.

If during the study any approved medication is started to treat NASH, the indication must be properly documented on the eCRF.

The following medications if required (and no alternative exists), will need to be discussed with the Sponsor:

- Drugs that may cause NAFLD (e.g. valproic acid, tamoxifen, methotrexate, amiodarone, chronic treatment with corticosteroids, high dose estrogen and tetracycline)
- Glucagon-like peptide-1 (GLP-1) receptor agonists
- Thiazolidinediones (TZDs)
- Vitamin E

## 7.3 Drug-Drug Interactions

A study in healthy subjects has shown no evidence of an interaction between Aramchol 300mg BID and the probe CYP3A4 substrate midazolam or atorvastatin which is also metabolized by this isozyme.

The potential for an effect of Aramchol on the anticoagulant activity of warfarin has not been studied; in light of its low therapeutic index, subjects receiving warfarin should have their INR monitored closely during the first few weeks of treatment with study drug.

The effects of strong inducers of CYP3A4 on concentrations of Aramchol have not been studied. To ensure adequate exposure to Aramchol, co-administration of enzyme inducers such as rifampicin, carbamazepine, phenytoin, enzalutamide and St. John's wort should be avoided.

For a detailed description of DDI assessment and studies refer to the current IB.

